## 1 Study details

**Protocol Title**

Understanding and maximizing the community impact of antimalarial treatment (INDIE-SMC)

**Study code**

INDIE-SMC

**Trial Register Identifier**

NCT05878366

**Sponsor (representative)**

[name]

London School of Hygiene and Tropical Medicine (LSHTM), United Kingdom

*Table 1: Abbreviations*

Abbreviation	Full form
AQ	Amodiaquine
CRF	Case Report Form
DEAQ	Desethylamodiaquine
DOT	Directly Observed Treatment
FGD	Focus Group Discussion
GRAS	Groupe de Recherche Action Santé
IDI	In-Depth Interview
IQR	Interquartile Range
KII	Key Informant Interview
LLIN	Long Lasting Insecticide Net
LSHTM	London School of Hygiene and Tropical Medicine
MoH	Ministry of Health
ODK	Open Data Kit
qRT PCR	Quantitative Real-Time Polymerase Chain Reaction
SAP	Statistical Analysis Plan
SMC	Seasonal Malaria Chemoprevention
SPAQ	Sulfadoxine-Pyrimethamine plus Amodiaquine

## 2 Study design

### 2.1 Introduction

The Statistical Analysis Plan (SAP) describes the statistical analyses of data obtained in the INDIE-SMC study. It is a controlled document and may be updated until the final analysis is performed.

### 2.2 Study rationale

Seasonal Malaria Chemoprevention (SMC) currently involves repeated administrations of sulfadoxine-pyrimethamine plus amodiaquine (SPAQ) to children below the age of 5 years during the peak transmission season in areas of seasonal malaria transmission. Whilst highly impactful in reducing the burden of *P. falciparum* malaria in controlled research

settings, the impact of SMC in terms of reducing infection prevalence is limited in real-life settings.

It is currently unclear whether failure of SMC with SPAQ to prevent malaria parasitaemia is associated with

- i) imperfect adherence;
- ii) parasite resistance to the drug components;
- iii) active drug concentrations that are achieved in SMC participants;
- iv) consistent exposure to reinfection.

It is also unclear whether extending the age-range targeted by SMC will reduce the infectious reservoir for transmission to a level where community-benefits may be expected. It is further currently unclear what factors determine (cascades in) efficacy decay and whether SMC coverage and uptake is equitable or affected by, for example, gender of children in the target age group. Quantifying each of these elements should contribute to understanding the effectiveness of SMC in programmatic settings.

### 2.3 Design & intervention

The study is designed to evaluate SMC effectiveness and consists of three interventional study arms, with the first arm receiving an intervention that is implemented as part of routine control.

Study arm 1:	SMC in children under the age of 5 years, implemented by the Ministry of Health (MoH) without directly observed treatment for the full course of SMC
Study arm 2:	SMC in children under the age of 5 years, with directly observed treatment for the full course of SMC
Study arm 3:	SMC in children under the age of 10 years, with directly observed treatment for the full course of SMC

SMC consists of SP and AQ administered daily for three days. SP is given on the first SMC day only while AQ is given daily over three days. In total 4 rounds of SMC will be conducted during the peak malaria transmission season from July to October, separated by approx. 30 days.

Each study arm contains 62 clusters; each cluster consists of 3 compounds where each compound has at least one child aged 3-59 months and one child aged 5-9 years. (186 compounds per arm; 558 compounds in total). Differences in SMC coverage and efficacy will be determined in the SMC-targeted age groups. In contrast, all age groups will take part in the evaluation of the study to assess the impact of the intervention on the infectious reservoir in the community and compare parasite carriage in targeted and untargeted populations. To detect possible behavioural contamination and differences in SMC uptake or adherence in study arm 1 compared to what would be observed if there would be no

study team present, a single cross-sectional survey 7 days after the last (4th) round of SMC coverage is assessed outside the study area (2-5 kilometres from the nearest enrolled study compound) by questionnaire and samples to determine plasma levels of SMC drugs and parasite carriage by qPCR. Plasma levels of SMCR drugs are used as the most definitive evidence of differences in SMC uptake/adherence.

Scheduled surveys and scheduled or unscheduled sampling timepoints will take place in each arm; these surveys are designed and timed for several outcome measures and include:

- i) a survey prior to first SMC roll-out (performed in all compounds).
- ii) mid-study surveys 3, 4 and 5 weeks after the last SMC roll out (each compound will participate in one of these surveys).
- iii) end-of-study survey up to 10 weeks after last SMC roll out (performed in all compounds).
- iv) sampling for drug metabolite assessment shortly after the last SMC round (sample collection in all compounds in the study arms and outside-study control area).
- v) sampling for transmission assay on first day of SMC round 2 to 4 (sampling in all compounds; selection from individuals aged 5-9 years).
- vi) passive case detection in all four health facilities that are accessed by the study population throughout the study period (from enrolment until the end of follow-up).

### **3 Randomization**

The unit of randomization will be the cluster; each cluster comprises of 3 compounds. Clusters are randomly allocated to one of the three study arms by a computer generated algorithm and stratified by village. Stratification by village was to account for spatial differences in malaria exposure, distance from health facilities, and treatment seeking behavior. In total, 185 clusters were randomized.

### **4 Study objectives**

The specific study objectives are to:

- i) compare SMC effectiveness in children aged 3-59 months as implemented by the national malaria control program and SMC implemented in a research context where all doses are directly observed.
- ii) Evaluate the effectiveness of SMC to reduce malaria infection prevalence in 5-9 year olds

- iii) quantify the infectious reservoir and the contribution of different age groups to transmission with conventional SMC (<5 years) and extended SMC (<10 years)
- iv) determine the impact of drug resistance (by molecular typing of *dhps*, *dhfr*, *pf crt* and *pfmdr1*) and drug absorption on SMC efficacy
- v) understand social barriers and enablers interfering with SMC efficacy and how SMC uptake is related to health equity with special attention to gender inequalities.
- vi) quantify SMC efficacy decay under programmatic conditions and key drivers of this decay.

## 5 Study endpoints

### 5.1 Primary endpoint

- Parasite prevalence by quantitative PCR (qPCR) at the end of the transmission season in age groups targeted by seasonal malaria chemoprevention. [end-of-study survey].

This endpoint will be compared between arms 1 and 2 (in children aged 3-59 months) and arms 2 and arm 3 (in children aged 5 years-9 years). [end-of-study survey].

### 5.2 Secondary endpoint

- Parasite prevalence by microscopy at the end of the transmission season in all age groups (between arm comparison). [end-of-study survey]
- Parasite prevalence by qPCR at the end of the transmission season in all age groups (between arm comparison). [end-of-study survey].
- Parasite prevalence by qPCR at the end of the transmission season compared between arms 1 and combined arms 2 + 3. [end-of-study survey].
- Parasite prevalence by microscopy prior to SMC rounds 2, 3 and 4 in SMC-targeted age groups (between arm comparison). [at SMC-delivery].
- Rate of re-infection with *P. falciparum* at weeks 3, 4 and 5 after the last round of SMC, assessed in SMC-targeted age groups (between arm comparison). [mid-study surveys].
- Gametocyte prevalence by qRT-PCR at weeks 3, 4 and 5 after the last round of SMC, assessed in SMC-targeted age groups (between arm comparison). [mid-study surveys].
- Gametocyte prevalence by qRT-PCR at the end of the transmission season in all age groups (between arm comparison). [end-of-study survey].
- Gametocyte prevalence by qRT-PCR at the end of the transmission season in age groups targeted by SMC (comparison between arm1 and 2 (in children aged 3-59 months) and arms 2 and arm 3 (in children aged 5 years-9 years)). [end-of-study survey].
- Plasma levels of AQ and desethylamodiaquine (DEAQ) after the 4th round of SMC in children aged 3 months-9 years (between arm comparison) [post-SMC round 4].
- Clinical malaria incidence captured during passive-case detection (between arm comparison) [[post-SMC round 4]

### 5.3 Exploratory endpoints

- Infectivity to mosquitoes, defined as the percentage of infected mosquitoes, in relation to gametocyte density and plasma drug levels of AQ and DEAQ (across arms assessment) [during and shortly after SMC rounds 2-4].
- Size and age-distribution of the infectious reservoir for malaria, defined as the likelihood that a mosquito becomes infected with malaria parasites after feeding on a population member (between arm comparison) [during the study].
- Prevalence of drug resistance markers in infected children aged 3 months-9 years assessed post each round of SMC (between arm comparison) [during the entire study].
- Description of perceived social barriers to SMC uptake [during the entire study].
- Quantification of SMC efficacy decay under programmatic conditions [during the entire study].

## 6 Study population

The study population will be all members of 555 compounds (185 clusters of 3 compounds) in Saponé Health District (Burkina Faso). Clusters are randomized over 3 study arms. Compound members of all ages will be included in study procedures (e.g. evaluation of the intervention) but only children will be targeted with the intervention. Based on census data, and recent studies in the same study area, an average of 1.5 children aged <5 years and 1.5 child 5-9 years per compound is expected (4.5 and 4.5 per cluster, respectively).

In addition, 120 randomly selected compounds outside of the study area are included for a single survey after the last round of SMC.

## 7 Sample size considerations

Evaluable study clusters will comprise 3 compounds and have between 4-5 children below 5 years of age (eligible for standard SMC) and similar numbers of children aged 5-10 years (eligible for SMC in study arm 3). We assume ~40% parasite prevalence detected by PCR at the end of the transmission season in children aged 5-10 without SMC and 16% parasite prevalence in children aged <5 years under programmatic SMC (based on recently completed work in the same area Collins, Ouedraogo et al. in prep). When assuming a reduction to 25% parasite prevalence in children aged 5-10 years when included in SMC, a sample size of 55 clusters per arm (x3 compounds per cluster and an estimated total 6 children in this age group per cluster) will achieve 87% power to detect this difference at an alpha of 0.05 and a coefficient of variation of 0.3 (data from INDIE 1a; LSHTM EC #14724; Centre National de Recherche et de Formation sur le Paludisme institutional review board (Deliberation N° 2018/000002/MS/SG/CNRFP/CIB; Burkina Faso national medical ethics committee (Deliberation N° 2018-01-010)). This sample size will also allow the detection of a reduction of parasite prevalence in directly observed SMC to 7% as

compared to 16% under programmatic SMC, in children under 5 years of age. The total number of compounds per arm has been increased to 62 to mitigate the effects of non-compliance and drop-outs and also for logistical reasons, such whole villages are included. We will thus enrol a total of 186 clusters over 3 arms in a ratio of 1:1:1 with 558 compounds in total. We anticipate that this will include a minimum of 720 children below 5 years of age (2 per compound, based on recent census data) and 720 children aged 5-9 years (1 per compound as per inclusion criterion).

For assessments of the human infectious reservoir, the intervention study is too large in scope (i.e. 558 compounds, compared to 180 in the previous INDIE project) and the time-window for transmission assays is too narrow (i.e. transmission assays are ideally done within weeks after SCM administration) to assess a direct impact of SMC on gametocyte infectivity with a conventionally powered comparison between arms. Thus a combination of methodologies (quantification of the association between gametocyte density and infectivity in the absence of treatment; imputed mosquito transmission from gametocyte density) are used (i, ii) It was further shown that direct comparisons of the association between gametocyte density and mosquito infection rates in mosquito feeding assays can demonstrate whether imputation is indeed acceptable across populations (i) or whether there are subpopulations with a different association (for example due to gametocyte-sterilizing effects of antimalarials (iii)). These insights will be used to perform mosquito feeding assays on gametocyte positive individuals with and without prior SMC and compare mosquito infection rates for a given gametocyte density (iii). Since the hypothesis is that SPAQ will permanently sterilize gametocytes, any reduced infectivity of gametocytes will remain apparent even after drug levels have waned (i.e. the gametocytes are permanently damaged by drug exposure) (iv). A possible sterilizing effect of SPAQ can be assessed by preferentially recruiting children who are gametocyte positive at the start of SMC and invite them for mosquito feeding post SMC. This will be done in children aged 5-9 years only who carry the highest parasite densities and highest gametocyte prevalence/density (i); this also avoids phlebotomy from the youngest children. A median gametocyte density of ~14 gametocytes/ $\mu$ L (IQR 1.8-44.2) as previously observed post-SMC (v, vi) is anticipated. Whilst the exact number of experiments that can be conducted will be dictated by mosquito husbandry, simulations indicate that when recruiting 100 children who received SPAQ (arm 3) and 100 children who did not (arms 1 & 2) and dissecting 40 mosquitoes per experiment, we would have >90% power to detect a 70% reduction in infectivity (vii).

An exact sample size justification for the single cross-sectional survey in the area outside the study-targeted population is complicated; this survey is performed to give a broad indication of the potential influence the presence of our study team may have on the operational delivery of SMC in arm 1. It is not part of any main comparisons. Estimates of adherence are based on questionnaire data, supported by measurements of DEAQ drug levels in plasma. In arm 2 and 3 (Directly Observed Treatment (DOT); by design full adherence), the median level of DEAQ at day 4 following the last dose of AQ is expected to be 550 ng/mL (IQR 350-850). Based on a large assessment of reported adherence and measured AQ/DEAQ plasma levels following SMC in Niger (viii), we anticipate that <50% of children show complete adherence in arms 1 and the control village and >20% of the children in these populations may fail to take any dose. If we conservatively assume that

this results in a reduction of median DEAQ levels to <400ng/mL (IQR 200-700), we can estimate the power to detect this difference when enrolling 120 children in the SMC-targeted age range in the control area. For this, we assume that these DEAQ levels stem from right-skewed (log-normal) distributions; giving median log DEAQ concentrations of 6.31 (IQR 5.86-6.75) for DOT and 5.99 (IQR 5.30-6.55) for non-DOT. If it is further assumed that the distribution of the logged values is normally distributed, we can estimate the standard deviation through the IQR as  $IQR/1.349$ , giving standard deviations of 0.93 and 0.66, respectively. Using a sample size of 120 per group, and a Welch's two sample t-test for testing the differences between the log DEAQ concentrations, we estimate a power of 86.3% to detect these differences. Based on these assumptions, we are confident that sampling 120 children <5 years of age will allow meaningful assessments. As indicated above, this sample size estimation is not relevant for any of the main comparisons in the study but merely used to ensure informative sampling and avoid exposing an unnecessarily large population to the small discomfort of a single finger prick sample. We will thus aim to determine plasma levels of at least 120 children <5 years in arm 1; 120 children <5 years from arms 2 and 3 combined and 120 children from the control area.

Drug plasma levels are also relevant for other comparisons (e.g. the impact on transmission efficiency in mosquito feeding assays, the role in explaining clinical malaria episodes and asymptomatic parasite carriage after SMC. For these comparisons, samples may be selected in a case-control manner.

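### The 87% power in SAP Section 7 does not follow from the stated 6 children per cluster (about 95%; 87% fits 4), the cluster size is stated inconsistently, and 720 children follows from neither rate given for it

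*SAP*

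**What the plan says.** SAP Section 7 sets out the power for the comparison of arms 2 and 3 in the older children:

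- Prevalence without SMC: "We assume ~40% parasite prevalence detected by PCR at the end of the transmission season in children aged 5-10 without SMC".
- Prevalence with SMC: "When assuming a reduction to 25% parasite prevalence in children aged 5-10 years when included in SMC".
- Number of clusters: "a sample size of 55 clusters per arm (x3 compounds per cluster".
- Between-cluster variation: "a coefficient of variation of 0.3".
- Children per cluster, with the resulting power: "estimated total 6 children in this age group per cluster) will achieve 87% power to detect this difference at an alpha of 0.05".

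The same section opens by giving evaluable clusters 4 to 5 children under 5 years and similar numbers in the older group. Section 6 agrees with that opening: "an average of 1.5 children aged <5 years and 1.5 child 5-9 years per compound is expected (4.5 and 4.5 per cluster, respectively".

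For under-fives (16% versus 7%, the other primary comparison in Section 5.1), Section 7 says only that the difference can be detected. It gives no power.

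Section 7 closes with 186 clusters and 558 compounds. It anticipates at least 720 children under 5, at 2 per compound, and "720 children aged 5-9 years (1 per compound as per inclusion criterion". Sections 3 and 6 give 185 clusters, and Section 6 gives 555 compounds.

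For the drug-level survey, Section 7 lists the DOT distribution of log DEAQ first and the non-DOT distribution second, "giving standard deviations of 0.93 and 0.66, respectively". It reports 86.3% power for that difference with 120 children per group.

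**The concern.** A power statement should be reproducible from the inputs printed beside it. Here one section implies three cluster sizes for the older children: 4-5, then 6, then 3 (1 per compound in 3 compounds). Section 6 adds 4.5. The total of 720 is attached to two different rates, so at least one attribution must be wrong.

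Both primary comparisons depend on this number. A reader cannot tell which cluster size the design rests on, or what power the under-five comparison was planned to have.

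**Working it through.** **Inputs.** p0 = 0.40, p1 = 0.25, c = 55 clusters per arm, k = 0.3, alpha 0.05 (all SAP Section 7). Two-sided testing and the Hayes-Bennett formula are assumptions, because the SAP states neither.

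**Formula.** Power = Φ(√{(c − 1)(p0 − p1)² / [p0(1 − p0)/m + p1(1 − p1)/m + k²(p0² + p1²)]} − 1.96), with m children per cluster.

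**The plan's own figure, m = 6.**
- Numerator: 54 × 0.15² = 1.215.
- Denominator: 0.24/6 + 0.1875/6 + 0.09 × (0.16 + 0.0625) = 0.0400 + 0.03125 + 0.020025 = 0.091275.
- √(1.215/0.091275) − 1.96 = 3.649 − 1.96 = 1.689, so power is 95.4%, not 87%.

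**m = 4.** Denominator 0.0600 + 0.046875 + 0.020025 = 0.1269. √(1.215/0.1269) − 1.96 = 3.094 − 1.96 = 1.134, so power is 87.2%. With 4 children, 55 is also the smallest number of clusters per arm that reaches 87%. With 6 children, about 40 would do.

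**Other readings at m = 6.**
- c in place of c − 1: 95.7%.
- Noncentral t: 95.4%.
- Design-effect forms with the ICC derived from k: 95.2% to 96.3%.
- One-sided alpha: 97.7%.
- Alpha 0.025: 92.0%.
- No clustering: 98.5%.
- 0.3 read as an ICC: 74.2%.

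None is within 2 points of 87%. To get 87% with 6 children, k would have to be about 0.51.

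**Both primary comparisons.** For 16% versus 7%, the same formula at m = 4 and c = 55 has numerator 54 × 0.09² = 0.4374. The denominator is (0.1344 + 0.0651)/4 + 0.09 × (0.0256 + 0.0049) = 0.05262. Power is Φ(2.883 − 1.96) = 82.2%.

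| Clusters per arm | m | 40% vs 25% | 16% vs 7% |
|---|---|---|---|
| 55 | 4 | 87% | 82% |
| 55 | 4.5 | 90% | 86% |
| 55 | 6 | 95% | 94% |
| 62 | 4.5 | 93% | 90% |

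**Totals.** 558 × 2 = 1116; 558 × 1 = 558; 558 × 1.5 = 837. With the 555 compounds of Section 6: 1110, 555 and 832.5. None is 720. Conversely, 720/558 = 1.29 per compound, or 720/186 = 3.87 per cluster. For ages 5-9 the reason given is the inclusion criterion, which Section 2.3 sets at a minimum of one child per compound. It therefore guarantees 558, not 720.

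**DEAQ standard deviations.** By the SAP's own IQR/1.349 rule, DOT is (6.75 − 5.86)/1.349 = 0.66 and non-DOT is (6.55 − 5.30)/1.349 = 0.93. The text prints them in reverse. With 120 per group the standard error is √[(0.66² + 0.93²)/120] = 0.104 whichever way they are labelled. The Welch power for the 6.31 − 5.99 = 0.32 difference reproduces at 86.3% to 86.4%.

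**The case against.** The strongest defence is that nothing here harms the trial. The 87% understates power at 4.5, 5 and 6 children and equals it at 4, the low end of Section 7's own range. That stands, and it limits the point to a reporting error.

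The 6 also has a plausible source: 3 compounds at the 2 per compound that Section 7 quotes for under-fives. One could read 6 as the total and 4 as the evaluable number. The SAP does not say so, and Section 6 expects 4.5 rather than 6. That 4 children were used is likewise an inference. Another route to about 87% is 5 children with alpha 0.025 (87.5%), but the SAP states 0.05.

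For under-fives, 720 is called a minimum. As a floor it is compatible with 1.5 or 2 children per compound. What fails is the stated derivation, most clearly for ages 5-9.

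A reader might infer that the trial is underpowered, since one child per compound gives 3 per cluster and 78% and 71% power with 55 clusters (83% and 76% with 62). The documents do not support this. Three is an eligibility floor that would be the mean only if every compound held exactly one child in the age group, whereas Section 6 expects 1.5.

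A reader might also infer that the 86.3% is wrong, or that the outside survey needs a prescribed detectable ratio. Neither follows. Transposing the standard deviations leaves the power unchanged, and Section 7 calls the survey a broad indication outside the main comparisons. Any figure for arm 1 versus the outside area needs an assumed spread in both groups. If the study team's presence lifted arm 1 to DOT-like adherence, the 86.3% would apply to that contrast too.

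**Conclusion.** The point holds as an error of statement. The 87% is about 8 points below what 6 children per cluster gives and matches 4. The cluster size is inconsistent within Section 7 and with Section 6. The 720 follows from neither rate attached to it.

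The power discrepancy is conservative for the older children, and the under-five comparison has no stated power to check. At the expected 4.5 children, power is 90% and 86% with 55 clusters per arm, so no shortfall is shown.

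The power figures assume the two-sided Hayes-Bennett formula. The contradictions in cluster size and totals need no formula. The transposed DEAQ standard deviations are a minor slip with no effect on the 86.3%.

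**What to change.** In SAP Section 7:

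- State the one cluster size used, with the formula and sidedness, and use it consistently with Section 6.
- Give power for both primary comparisons on that size. With 4 children and 55 clusters: 87% and 82%. With 4.5 children: 90% and 86% at 55 clusters, 93% and 90% at 62.
- Replace both 720 totals with numbers that follow from the stated rate and the 185 clusters and 555 compounds of Sections 3 and 6. At 1.5 per compound this is about 832 per age group (555 × 1.5 = 832.5), with 555 as the eligibility floor.
- Print the DEAQ standard deviations as DOT 0.66 and non-DOT 0.93. Say that the 86.3% is for DOT versus non-DOT, not for arm 1 versus the outside area when both have non-DOT adherence.

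The cost is a wording change in the SAP. Recruitment, data collection and analysis are untouched.

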#### **Exploratory endpoints**

*12. Infectivity to mosquitoes, defined as the percentage of infected mosquitoes, in relation to gametocyte density and plasma drug levels of AQ and DEAQ (across arms assessment) [during and shortly after SMC rounds 2-4].*

The association between proportion of infected mosquitoes and gametocyte density will be determined using generalized linear models assuming a binomial distribution with a log-link for participants with and without detectable AQ/DEAQ plasma concentrations. In addition, infectivity will be compared between individuals with/without AQ/DEAQ plasma levels using a previously published statistical model (ix). In case of low infectivity, the nonparametric van Elteren's test, an extension of the Wilcoxon rank sum test that compares groups in a stratified manner will be used (iii) where we compare infectivity between groups after stratifying in gametocyte density categories. Infectivity is then compared within different bins to test for differences between arms, accounting for gametocyte density. Additional analyses will take into consideration AQ/DEAQ concentrations at continuous scale (rather than simple detectability).

*13. Size and age-distribution of the infectious reservoir for malaria, defined as the likelihood that a mosquito becomes infected with malaria parasites after feeding on a population member (between arm comparison) [during the study].*

The size and shape of the infectious reservoir will be estimated using a combination of directly observed mosquito infection events and imputed transmissibility (i, ii). This imputed transmissibility will use gametocyte density (measured for all relevant timepoints) as starting point. The association between proportion of infected mosquitoes and gametocyte density will be determined using generalized linear models assuming a binomial distribution with a log-link. If drug levels do not influence infectivity (see 8), a

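### Endpoint 12 compares mosquito infectivity across feeds spread over SMC rounds 2-4 but names only gametocyte density as adjustment; round should be added

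*SAP*

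**What the plan says.** **Timing.** SAP section 2.3 lists "sampling for transmission assay on first day of SMC round 2 to 4", in all compounds, with selection from children aged 5-9 years. The same section puts successive rounds about 30 days apart.

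**Numbers.** Section 7 gives the scenario "simulations indicate that when recruiting 100 children who received SPAQ (arm 3) and 100 children who did not (arms 1 & 2"), with "dissecting 40 mosquitoes per experiment", and concludes "we would have >90% power to detect a 70% reduction in infectivity". It qualifies this: "Whilst the exact number of experiments that can be conducted will be dictated by mosquito husbandry". Children who are gametocyte positive are recruited by preference. No split by round is given, and nothing requires the two groups to be fed concurrently.

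**Analysis.** Section 10.7, endpoint 12, names three methods:
- a binomial GLM with log link for the proportion of infected mosquitoes on gametocyte density, for children with and without detectable AQ/DEAQ;
- a published model (reference ix);
- if infectivity is low, a van Elteren test in which "we compare infectivity between groups after stratifying in gametocyte density categories".

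A further analysis uses drug concentration on a continuous scale. Round, date, feeding session and mosquito batch are not named. For endpoint 1, by contrast, the SAP does name its design terms (cluster and village).

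**Onward use.** Under endpoint 13, one density-infectivity curve is used if drug levels do not influence infectivity. If their effect is statistically significant, reservoir estimates within one month of SMC take study arm into account. The cross-reference there is to item 8, which I read as endpoint 12.

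**The concern.** Randomization does not balance feeding rounds between the groups. The children fed are chosen after randomization, on gametocyte positivity, from one arm for the treated group and two arms for the untreated group. The two groups could therefore be spread differently over three rounds that cover much of a transmission season.

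Infectivity at a given gametocyte density may change between rounds, for example with season or with the condition of the mosquito colony. If the round mix also differs, a density-only comparison attributes part of that change to SPAQ. It can produce an apparent sterilizing effect or hide a real one, and the significance decision then carries into how endpoint 13 is estimated.

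**Working it through.** **1. The plan's own figure.** The power above 90% cannot be reproduced strictly, because the SAP gives no baseline infectivity, within-child correlation or alpha for this comparison. It is plausible. I simulated 100 v 100 children with 40 mosquitoes each and a true ratio of 0.30.
- From section 7: "A median gametocyte density of ~14 gametocytes" per microlitre, IQR 1.8-44.2. If log-normal, the SD of ln density is (ln 44.2 - ln 1.8)/1.349 = 2.37.
- Assumed: infectivity at the median density 3-15%, within-child correlation 0.1-0.3, density slope 0.4 on the log scale, two-sided alpha 0.05.
- Analysis: log-link mean model with robust standard errors, 600 runs per setting.

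Power exceeded 90% in 9 of 12 settings. The exceptions were 3% infectivity with correlation 0.2 (84%) or 0.3 (69%), and 5% with 0.3 (88%).

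**2. Can the round mix differ?** The relative size of the recruitment pools, using the only prevalences the SAP gives for this age group (section 7: 40% without SMC, 25% with), is 2 x 0.40 / 0.25 = 3.2 untreated to 1 treated. At equal prevalence it is 2.0. These are end-of-season PCR parasite prevalences, so they only stand in for gametocyte positivity at rounds 2-4. They show that unequal recruitment speed is credible, not that it will happen.

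**3. Size of the bias, by formula.** With no SPAQ effect, let infectivity at a given density change by a factor r per round, with k = 0, 1, 2 for rounds 2, 3, 4. The spurious treated/untreated ratio is Σ(w_T r^k) / Σ(w_U r^k). Assumed mix: treated feeds even over rounds, untreated 60/30/10%.

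For r = 0.7: (1 + 0.7 + 0.49)/3 = 0.730; 0.6 + 0.3 x 0.7 + 0.1 x 0.49 = 0.859; ratio 0.730/0.859 = 0.85.

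| r per round | Spurious ratio |
|---|---|
| 0.6 | 0.80 |
| 0.7 | 0.85 |
| 0.8 | 0.90 |
| 1.0 | 1.00 |
| 1.25 | 1.12 |
| 1.5 | 1.24 |

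**4. Does adding round remove it?** Same simulation, no SPAQ effect, 10% infectivity at the median density, within-child correlation 0.2. Cells show the median ratio and the type I error. Mild mix: treated 25/35/40%, untreated 45/35/20%. Strong mix: treated 20/30/50%, untreated 60/30/10%.

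| Round mix | Infectivity, rounds 2/3/4 | Density only | Density + round |
|---|---|---|---|
| Equal | 1 / 0.75 / 0.5 | 0.997, 5.0% | 1.005, 4.8% |
| Mild | 1 / 0.75 / 0.5 | 0.880, 10.5% | 1.009, 6.7% |
| Mild | 1 / 0.5 / 0.25 | 0.767, 20.3% | 0.986, 5.2% |
| Mild | 1 / 1.5 / 2 | 1.135, 15.0% | 0.997, 5.7% |
| Strong | 1 / 0.75 / 0.5 | 0.769, 31.7% | 1.000, 7.2% |
| Strong | 1 / 0.5 / 0.25 | 0.616, 59.5% | 0.995, 5.0% |
| Strong | 1 / 1.5 / 2 | 1.290, 51.3% | 1.003, 8.5% |

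The simulation error on a 5% rate is about √(0.05 x 0.95/600) = 0.9 percentage points. The bias is therefore removed, while a little excess type I error remains in some settings.

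**5. Against the planned effect.** With a true ratio of 0.30, unequal mixes move the density-only estimate to between 0.18 and 0.40. Power in these settings stays at 94% or more with or without round. A small effect is more exposed: a true 20% reduction with a spurious factor of 1.24 would appear as 0.80 x 1.24 = 0.99.

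**The case against.** A reader might infer that recruitment runs to fixed quotas, so that the untreated group fills within one round while arm 3 must continue, and treatment is confounded with round by construction. On the SAP's figures (4.5 children aged 5-9 per cluster, 62 clusters per arm) this looks arithmetical: 558 x 0.40 = 223 infected untreated children against 279 x 0.25 = 70 treated, so 100 feeds need 45% of one pool and 143% of the other. The documents do not support that reading:

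- 100 v 100 is a power scenario, and section 7 leaves the number of experiments to mosquito supply. If feeding capacity is the limit, the pool of infected children does not set the pace.
- Gametocyte prevalence at rounds 2-4 is given nowhere. If fewer than 45% of infected untreated children were gametocyte positive and fed, that group would also spread over rounds.
- The 143% is sensitive. With the 6 children per cluster that section 7 also uses, it is 100/(6 x 62 x 0.25) = 108%.
- All compounds are sampled at each round, so concurrent comparators are available.

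Other points also stand. The round mixes and round-to-round changes above are assumptions. The terms of the published model cannot be checked from the SAP. Both endpoints are exploratory, and section 7 disclaims a conventionally powered comparison between arms. The effect on endpoint 13 is limited to estimates within one month of SMC, since the end-of-study reservoir assumes no drug effect in any case.

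What the objection does not remove is that the GLM and the van Elteren test, as written, would not correct an imbalance if one occurred.

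**Conclusion.** The point holds as a minor one. Density is the only factor that the named GLM and the fallback test account for, feeds span three rounds about a month apart, and no balance by round is set. Bias needs two conditions together: a round mix that differs between the groups, and infectivity at a given density that changes between rounds. The SAP neither establishes nor excludes either.

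Under the assumptions in step 3, a null effect would appear as a ratio of roughly 0.8 to 1.25. More extreme values, such as 0.62 with a type I error near 60%, need both a strong imbalance and a steep trend. With an equal mix there is no bias.

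A reader might also infer that the planned contrast is invalid. It is not: a 70% reduction would still be detected in the imbalance settings examined, although its estimated size would shift. The practical exposure is a false or missed smaller effect, and through it the choice of curve for the endpoint 13 estimates within one month of SMC.

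**What to change.** - **Section 10.7, endpoint 12:** add SMC round as a fixed effect, or feeding session as a random intercept, to the GLM. State whether the published model allows for either.
- **Endpoint 13:** use the same term when fitting the density-infectivity curve.
- **van Elteren test:** stratify by round as well as density, with coarser density bins if strata become sparse.
- **Section 7:** state that, where feasible, children with and without prior SPAQ are fed in the same rounds.

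The analysis changes are wording plus a few parameters, and in the simulations they cost little power. Round follows from the sampling schedule. The SAP does not say that feed date or session is recorded, so that should be confirmed before session is used. Concurrent feeding is a field matter, hence only where feasible.

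Adjustment cannot replace it entirely. If all untreated feeds fell in round 2 and treated feeds were even over rounds, only about 100/3 = 33 treated feeds would have comparators in their own round, and the rest would contribute little to the contrast. Finer strata also weaken the van Elteren test, which the SAP reserves for low infectivity.
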